2.4. Study Rationale

Recently, CDK4/6 inhibition in combination with the anti-estrogen fulvestrant was found in a randomized phase III study to prolong the progression free survival of patients with advanced hormone receptor positive, HER2 negative breast cancer refractory to previous endocrine therapy compared to fulvestrant alone, irrespective of the menopausal status of patients enrolled in the study¹. A prolonged progression free survival was also found in a randomized phase II study in combination with letrozole in the front-line setting compared to letrozole alone². Abemaciclib has demonstrated significant improvement in PFS in combination with fulvestrant and with letrozole in the MONARCH 2 and MONARCH 3 studies leading to its approval in the post endocrine therapy and also, frontline setting for hormone receptor positive, HER2 negative breast cancer ^{23,24}. The basis of this synergy involves the dependence of estrogen receptor

positive breast cancers to CDK4/6 for growth and proliferation. Additionally, activation of growth factor receptor signaling is a hallmark for endocrine therapy resistance.

A similar hormone-driven cancer akin to breast cancers is prostate cancer. These tumors are driven by androgen receptor signaling, and CDK4/6 has also been found to be a bona fide target preclinically for advanced prostate cancer cell models³. Moreover, CDK4/6 inhibition can act as a radiation sensitizer through its effects on the DNA damage response and interactions with cell cycle pathway proteins^{4,5}. For example, it has been found that expression of DNA repair proteins can be regulated by E2F, a transcription factor necessary for the G1 to S phase transition⁶. Also, cyclin D1 has been found to exert a direct role on dna repair⁷⁻⁹. Lastly, CDK4/6 inhibition has been found to modulate the DNA damage response¹⁰. These data support the use of CDK4/6 inhibitors as a modulator of DNA damage to enhance sensitivity to radiation.

Given the role of CDK4/6 in tumor resistance to endocrine therapy, in activation of the DNA damage response, and in promoting radiation resistance, we hypothesize that the targeting of CDK4/6 with abemaciclib will enhance the cytotoxicity in combination with blockade of the androgen receptor pathway. Therefore, we propose a pilot phase II investigator initiated trial in patients with high-risk prostate cancer patients testing the tolerability and toxicity of abemaciclib in combination with ADT.

2.5. Population to be Studied

Patients with high risk localized or locally advanced prostate cancer who will be eligible for definitive treatment with Radiation therapy and ADT.

2.6. Potential Risks and Benefits to Human Patients

2.6.1. Potential Risks

Abemaciclib

Based on clinical experience with abemaciclib, the adverse events of special interest (AESIs) are neutropenia, infections, diarrhea, blood creatinine increased, hepatic events (increases in aspartate aminotransferase [AST] and alanine aminotransferase [ALT]), and embolism (mainly pulmonary embolism and deep vein thrombosis); furthermore, interstitial lung disease/pneumonitis is considered an adverse event (AE) of note.

Computed Tomography (CT) Scans

Patients will be exposed to a relatively small amount of radiation as a result of the CT scans required in this study. This degree of exposure has not been associated with harmful health effects. In addition, the frequency of CT scans performed in this study is similar to the standard of care frequency. Patients with a medical contraindication to CT scans or known iodinated contrast allergies may instead undergo magnetic resonance imaging (MRI). There is minimal risk of MRI imaging in patients able to undergo this type of exam including very rare reports of gadolinium-induce nephrogenic systemic fibrosis in patients with poor renal function.

MRI-US imaging.

Patients will undergo MRI-US fusion imaging pre-treatment and at 6 months post RT with comparison with historical controls receiving RT + ADT. There is minimal risk of MRI imaging in patients able to undergo this type of exam including very rare reports of gadolinium-induce nephrogenic systemic fibrosis in patients with poor renal function.

Prostate biopsy

Patients will have undergone MRI-US guided biopsy of the prostate at the time of diagnosis and archived tumor tissue will be used at screening for baseline analysis. An optional biopsy will be scheduled at 6 months post RT for tumor tissue profiling to identify association of molecular profile with PSA decline at 1 year. Risks include but are not limited to bleeding from biopsy site, increased risk of infection and complications related to anesthesia for the procedure.

Venipuncture

Patients could also experience side effects from venipuncture for tests that will be done as part of this study, including pain, tenderness, and bruising at the site of collection, and rarely infection may occur at the spot where the needle is inserted.

Other Risks

This study treatment may involve risks to unborn children and therefore patients should not father a baby while participating in this study.

Men must agree to use 2 effective and highly reliable methods of contraception at the same time (i.e., vasectomy, male latex condom with or without spermicide, partner's tubal sterilization, partner's use of an IUD, partner's use of diaphragm with spermicide, cervical cap with spermicide, or vaginal sponge that contains spermicide) during study treatment (including temporary breaks from treatment), and for at least 180 days after stopping Abemaciclib. The long-term risk of infertility is unknown.

Potential Benefits

Abemaciclib is an investigational product and its efficacy in combination with ADT has not been established. ADT is approved for treatment of localized or locally advanced prostate cancer. It is expected that the administration of Abemaciclib and ADT may result in clinical benefit (i.e. Tumor response).

2.7. Justification of the Dose, Schedule, and Route of Administration

The dose, schedule, and route of administration of Abemaciclib (150 mg BID) was selected based on safety, pharmacokinetics, and evidence of activity in the Phase 1b study (JBIF). Dose reduction is possible for treatment of adverse events, including anemia. Refer to section 6.3.1, Table 4 and section 6.3.3

ADT with LHRH analogues will be administered at Standard of care doses.

2.8. Study Conduct

This clinical trial will be conducted in compliance with the protocol, Good Clinical Practice (GCP), and the applicable regulatory requirements.

3. TRIAL OBJECTIVES AND PURPOSE

The purpose of this study is to evaluate the safety and tolerability of Abemaciclib in combination with ADT.

Primary Objective:

- To assess clinical response rates using
 - Proportion of patients with PSA nadir of ≤ 0.5 ng/ml on treatment

Secondary Objectives:

- Proportion of patients with PSA declines prior to radiotherapy
- Time to PSA failure
- To study the tolerability and feasibility of combining Abemaciclib with ADT for localized high risk or locally advanced prostate cancer.

Exploratory Objective:

- 1) MRI-US fusion imaging pre-treatment and at 6 months post RT with comparison with historical controls receiving RT + ADT.
- 2) Baseline (mandatory) and 6 months (optional) post RT tumor tissue profiling (MRI-US fusion guided) to identify association of molecular profile with PSA decline at 1 year.
- 3) Baseline, pre-radiotherapy and 6 months post-RT blood collection and profiling for molecular analysis.

4. INVESTIGATIONAL PLAN

4.1. Overall Study Design and Plan

4.1.1. Overview

This is a single center, Phase II, single arm, open-label study of Abemaciclib in combination with ADT in patients with localized high-risk or locally advanced prostate cancer who are eligible for definitive RT and ADT.

All patients must sign and date a consent form prior to undertaking any study-related procedures. Prospective patients will be screened to determine if they qualify for the study within 28 days of enrollment. Patients will receive ADT with LHRH analogues every 3 months and will receive Abemaciclib starting on C1D1 at 150 mg PO BID for 28 day cycles Table 3 (see Abemaciclib Administration [Section 6.1.4](#) and ADT Administration). Patients receive ADT x 2 years and will start 3 months before RT. Abemaciclib will start with initiation of ADT and pause 2 weeks prior to start of RT. Abemaciclib will resume with the first ADT administration post-radiation, which typically is at 1 month post radiation therapy. Abemaciclib and ADT will continue for a total ADT period of 24 months (+/- 3 days to allow for holidays and weekends). Patients will have laboratory evaluation every 2 weeks for the first 2 months and monthly thereafter for the next 2 months. Patients are also seen and evaluated every 4 weeks with laboratory evaluation. Labs may be drawn at outside laboratories at the PI's discretion.

Patients will receive study treatment until development of toxicity or disease progression on treatment or any reasons of withdrawal or a maximum of 24 months of therapy with ADT. Adverse events will be graded according to the National Cancer Institute (NCI) Common Terminology Criteria for Adverse Events (CTCAE) Version 4.03.

All patients will receive Abemaciclib at 150 mg BID PO dose. The trial is carried out in two stages. In stage I, a total number of 5 patients are accrued. If there are 0 response (PSA< 0.5) among these 5 patients, the study will be early stopped. Otherwise, additional 18 patients will be accrued in stage II, resulting in a total number sample size of 23. If there are 4 or more responses (PSA< 0.5) among these 23 patients, we reject the null hypothesis and claim that the treatment is promising. The design controls the type I error rate at one-sided 0.025 and yields the power of 80%. If we reject the null hypothesis, seven additional patients will be enrolled to explore the association between biomarkers and clinical activities. To account for 10% screen failure, total of 33 patients will be recruited to the study.

Table 1: Toxities leading to withdrawal of subjects

Toxicity Category	Drug-Related Toxicity/Grade
Hematologic	Grade 4 neutropenia for ≥ 5 days
	Febrile neutropenia: ANC $< 1000/\text{mm}^3$ with a single temperature of $>38.3^\circ\text{C}$ (101°F) or a sustained temperature of $>38^\circ\text{C}$ (100.4°F) for more than one hour.
	Neutropenic infection: Grade ≥ 3 neutropenia with Grade ≥ 3 infection
	Grade ≥ 4 Anemia
	Grade ≥ 4 thrombocytopenia or Grade ≥ 3 thrombocytopenia with Grade ≥ 3 hemorrhage
Non-hematologic	Grade 2 ($>3.0 \times \text{ULN}$) ALT/AST with total bilirubin $>2 \times \text{ULN}$, in the absence of cholestasis Grade 3 or 4 non-hematologic toxicity with the following exceptions: 
Asymptomatic electrolyte abnormality that resolve within 48 hours.Grade 3 headache lasting <48 hours

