definitive RT+ADT. Simon's optimal two-stage design (Simon, 1989) will be used for conducting the trial. The null hypothesis is that the proportion of patients with PSA <0.5 without any treatment is 5%, and the alternative hypothesis is that the proportion of patient with PSA <0.5 at 6 weeks into treatment is 30% or higher. The trial is carried out in two stages. In stage I, a total number of 5 patients is accrued. If there are 0 response (PSA < 0.5) among these 5 patients, the study will be early stopped. Otherwise, additional 18 patients will be accrued in stage II, resulting in a total number sample size of 23. If there are 4 or more responses (PSA < 0.5) among these 23 patients, we reject the null hypothesis and claim that the treatment is promising. The design controls the type I error rate at one-sided 0.025 and yields the power of 80%. If we reject the null hypothesis, seven additional patients will be enrolled to explore the association between biomarkers and clinical activities. Patients receive ADT x 2 years and will start 3 months before RT. Abemaciclib will start with initiation of ADT and pause 2 weeks prior to start of RT. Abemaciclib will resume with the first ADT administration post-radiation, which typically is at 1 month post radiation therapy. Abemaciclib and ADT will continue for a total ADT period of 24 months. Patients will have laboratory evaluation every 2 weeks for the first 2 months and monthly thereafter for the next 2 months. Patients are also seen and evaluated every 4 weeks with laboratory evaluation. Labs may be drawn at outside laboratories at the PI's discretion. For toxicity or adverse event, patients will undergo labs, physical examination and grades of toxicities will be determined using NCI CTCAE version 4.03. Disease response and biochemical failure will be assessed by PSA prior to the start of radiation and every 3 months following the end of radiotherapy and by the investigator (physical exam). The determination of disease progression for the study requires a confirmation of 3 consecutive rises of PSA 3 months apart in the setting of testosterone recovery. Patients will be withdrawn from study for following toxicities,

Toxicity Category	Drug-Related Toxicity/Grade
Hematologic	Grade 4 neutropenia for ≥ 5 days
	Febrile neutropenia: ANC < 1000/mm ³ with a single temperature of $>38.3^{\circ}\text{C}$ (101°F) or a sustained temperature of $\geq 38^{\circ}\text{C}$ (100.4°F) for more than one hour.

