	Neutropenic infection: Grade ≥ 3 neutropenia with Grade ≥ 3 infection
	Grade ≥ 4 Anemia
	Grade ≥ 4 thrombocytopenia or Grade ≥ 3 thrombocytopenia with Grade ≥ 3 hemorrhage
Non-hematologic	Grade 2 ($>3.0 \times \text{ULN}$) ALT/AST with total bilirubin $>2 \times \text{ULN}$, in the absence of cholestasis Grade 3 or 4 non-hematologic toxicity with the following exceptions: 
 • Asymptomatic electrolyte abnormality that resolve within 48 hours.

	
 • Grade 3 headache lasting <48 hours
Number of Patients (planned):	
30 patients with localized or locally advanced prostate cancer will be enrolled in the study.	
Diagnosis and Main Criteria for Inclusion:	

Inclusion Criteria:
 
 1. Histologically confirmed (core biopsy proven) adenocarcinoma of prostate, localized high-risk or locally advanced. 2. One of the below: 
 • Gleason 7-8, any T-stage, and PSA > 20, • Gleason 8, \geq T2, any PSA, • Gleason 9-10, any T-stage, any PSA • T3, any Gleason, any PSA • Positive pelvic lymph nodes are permitted. 3. Available biopsy of primary tumor or resected tumor specimen with adequate samples. 4. Prior treatment with systemic anti-cancer agents is not allowed. 5. ECOG PS = 0 or 1 6. Must have at least 1 target lesion 7. Life expectancy > 6 months 8. Adequate hematologic and end-organ function 
 • ANC \geq 1500/mm³ • Platelet count \geq 100,000/mm³ • Hb \geq 8g/dl • Creatinine \leq ULN or Creatinine Clearance (CrCl) \geq 60 ml/min • Total Bilirubin \leq 1.5 x ULN (except subjects with Gilbert syndrome, who can have total Bilirubin < 2.0 x ULN and direct bilirubin within normal limits are permitted) • AST and ALT \leq 3.0 x ULN 9. Agreement to remain abstinent or use appropriate contraception. 10. Willingness and ability to consent for self to participate in study. 11. Willingness and ability to comply with scheduled visits, treatment plan, laboratory tests, and other study procedures. 	
Exclusion Criteria:	

 1. Prior treatment with CDK 4/6 inhibitor. 2. Prior treatment with systemic agents or radiation treatment for the primary cancer. 	

3. Major surgical procedure or significant traumatic injury within 4 weeks prior to study treatment, and must have fully recovered from any such procedure.

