Hematologic toxicities including neutropenia, leukopenia, anemia, and thrombocytopenia have been observed in patients treated with abemaciclib, and causality has been established. Severe (Grade 3 and 4) neutropenia was observed in patients receiving abemaciclib. Patients should be monitored closely for signs of infection, anemia, and bleeding. **Table 9 provides guidance on dose modification and management of hematologic toxicities.**

Table 9: Dose Modification and Management — Hematologic Toxicities

Monitor complete blood counts prior to the start of abemaciclib therapy, every 2 weeks for the first 2 months, monthly for the next 2 months, and as clinically indicated.	
CTCAE Grade	Abemaciclib Dose Modifications
Grade 1 or 2	No dose modification is required.
Grade 3	Suspend dose until toxicity resolves to \leq Grade 2. Dose reduction is not required.
Grade 3, recurrent, or Grade 4	Suspend dose until toxicity resolves to \leq Grade 2. Resume at next lower dose.
Patient requires administration of a blood cell growth factor	Suspend abemaciclib dose for at least 48 hours after the last dose of blood cell growth factor and until toxicity resolves to \leq Grade 2. Resume abemaciclib at next lower dose unless the dose was already reduced for the toxicity that led to the use of the growth factor.

General Guidance for Non-hematologic Toxicities (excluding diarrhea, ILD/Pneumonitis and increased ALT/AST) Monitoring

Table 10: Dose Modification and Management — Non-hematologic Toxicities Excluding Diarrhea and ALT Increased

CTCAE Grade	Abemaciclib Dose Modifications
Grade 1 or 2	No dose modification is required.
Persistent or recurrent Grade 2 toxicity that does not resolve with maximal supportive measures within 7 days to baseline or Grade 1	Suspend dose until toxicity resolves to baseline or Grade 1. Resume at next lower dose.
Grade 3 or 4	

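### Table 1 withdraws patients for three severe drug-related toxicities after which Tables 7 and 9 resume abemaciclib at a lower dose, and nothing says which rule governs

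*Combined protocol and SAP*

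**What the plan says.** The synopsis introduces its toxicity list with "Patients will be withdrawn from study for following toxicities". Section 4.1.1 repeats the list as Table 1, titled "Toxities leading to withdrawal of subjects". The column heading limits it to drug-related toxicity, and no cycle or time window is given. Three entries matter here:

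- "Grade ≥ 4 Anemia"
- "Grade ≥ 4 thrombocytopenia or Grade ≥ 3 thrombocytopenia with Grade ≥ 3 hemorrhage"
- "Grade 3 or 4 non-hematologic toxicity with the following exceptions", the exceptions being a short-lived asymptomatic electrolyte abnormality and a Grade 3 headache of under 48 hours.

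Section 6.4.3 gives dose-modification rules for abemaciclib. The text before Table 9 states that "Hematologic toxicities including neutropenia, leukopenia, anemia, and thrombocytopenia have been observed in patients treated with abemaciclib" and that "Table 9 provides guidance on dose modification and management of hematologic toxicities". For the row "Grade 3, recurrent, or Grade 4", Table 9 suspends the drug until the toxicity is Grade 2 or lower and then resumes at the next lower dose. Table 7 likewise suspends and resumes at the next lower dose for Grade 3 ALT/AST that has not settled within 7 days.

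Section 6.5 requires permanent discontinuation for unacceptable toxicity or for failure to recover in 2 weeks, and allows continuation with the medical monitor's approval. It does not cite Table 1. The withdrawal list in section 5.3 does not contain or cite the Table 1 toxicities either.

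**The concern.** A patient withdrawn under Table 1 cannot also resume abemaciclib under Table 7 or Table 9. For the same event, two investigators could take opposite actions, each following a written instruction. At stake is whether the drug is restarted after a severe toxicity attributed to it, which should not depend on the page consulted.

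The statistical consequence is narrower. Section 10.2.2 plans to report the number and percentage of patients with adverse events resulting in study drug discontinuation, which bears on the tolerability objective in section 3. That figure would partly reflect which rule was applied as well as how well the drug was tolerated.

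A second ambiguity compounds this. The synopsis speaks of withdrawal from the study and the Table 1 title only of withdrawal of subjects, whereas the mandatory lists in sections 5.3 and 6.5 concern study treatment.

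**Working it through.** **Step 1. Do the scopes overlap?** Table 1 covers drug-related toxicity. Table 4 (section 6.4.1), which defines the allowed reductions, covers toxicity attributed to abemaciclib. An abemaciclib-related event therefore falls under both. Table 1 itself places an ALT/AST entry in its non-hematologic block, and section 6.4.2 counts laboratory abnormalities as non-hematologic toxicity, so Grade 3 ALT/AST is within Table 1's non-hematologic row.

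**Step 2. Compare the actions.**

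| Drug-related event | Table 1 and synopsis | Section 6.4.3 | Result |
|---|---|---|---|
| Grade 4 anemia | withdraw | Table 9: suspend, resume lower | conflict |
| Grade 4 thrombocytopenia | withdraw | Table 9: suspend, resume lower | conflict |
| Grade 3 ALT/AST unresolved at 7 days | withdraw | Table 7: suspend, resume lower | conflict |
| Grade 4 ALT/AST | withdraw | Table 7: discontinue | agree |
| ALT/AST above 3 x ULN with bilirubin above 2 x ULN, no cholestasis | withdraw | Table 7: discontinue | agree |
| Grade 3 or 4 ILD/pneumonitis | withdraw | Table 6: discontinue | agree |
| Grade 3 or 4 diarrhea; other non-hematologic toxicity | withdraw | Table 5; dose-modification Table 10: action cell blank in the text available | not assessed |

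Six rows in Tables 5, 6, 7 and 10 address Grade 3 or 4 non-hematologic toxicity: 1 resumes, 3 discontinue and 2 are blank in the extracted text. With the two cytopenias in Table 9, the explicit conflicts number 2 + 1 = 3.

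Two limits apply. Table 4 gives a single reduction step (150 to 100 mg BID), so a next lower dose is defined only for a patient still at 150 mg BID; no conflict is asserted for a patient already reduced. The neutropenia triggers and thrombocytopenia with hemorrhage are also left out of the count, because they can be read as narrower conditions layered on Table 9.

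**Step 3. Look for a precedence rule.** Sections 2.7, 5.3, 6.4.1, 6.4.2 and 6.5 contain none. Section 6.4.2 withholds both drugs for drug-related Grade 4 hematologic and Grade 3 or higher non-hematologic toxicity and requires notification before restart. Withholding can precede withdrawal, so this is supporting evidence only. Section 6.5 acts on non-recovery and leaves open a toxicity that recovers within 2 weeks. Section 2.7 refers to sections 6.3.1 and 6.3.3 for dose reduction; 6.3.1 is the radiotherapy target volume and 6.3.3 does not exist.

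**Step 4. Size.** The plan gives no figure to reproduce. If *k* patients have one of the three events and would stop under one rule but not the other, the discontinuation percentage shifts by at most *k/n*. Here *n* is the safety population (section 10.1.1: all who receive any abemaciclib). The sample sizes come from section 10.1, assuming every enrolled patient is treated.

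| *k* (assumed) | *n* = 30 | *n* = 23 |
|---|---|---|
| 0 | 0 | 0 |
| 1 | 1/30 = 3.3 points | 1/23 = 4.3 points |
| 2 | 2/30 = 6.7 | 2/23 = 8.7 |
| 3 | 3/30 = 10.0 | 3/23 = 13.0 |

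If the trial stops after stage I, *n* = 5 and one patient can move the figure by up to 1/5 = 20 points. The shift is 0 for a patient who would stop under either rule: no recovery in 2 weeks without approval to continue, stopped on the investigator's judgement, or resumed and later discontinued for an adverse event.

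**The case against.** The best defence is that the two sets of rules differ in force. The synopsis wording is mandatory, whereas Table 9 is presented as guidance and Table 4 as allowable reductions. On that reading the specific mandatory list sits above the general guidance, and a site that withdraws the patient complies with Table 1 and is covered by investigator judgement under sections 5.3 and 6.5. That reading is available, but the protocol does not state it. The table cells are instructions to resume, and a site following them breaks Table 1.

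A second objection is that if the neutropenia triggers can be layered on Table 9, so can Grade 4 anemia and thrombocytopenia. The cases differ. Table 1 takes Grade 4 neutropenia only when it lasts 5 days or more, which leaves Table 9 the shorter episodes. It takes every drug-related Grade 4 anemia and thrombocytopenia, so Table 9's Grade 4 instruction has nothing left to govern for those two. A reader who rejects the layering would count more than three conflicts.

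Third, Table 1 might be read as defining the unacceptable toxicity of section 6.5. Nothing links them, and section 6.5 would still not say that Table 1 overrides Tables 7 and 9.

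Two points stand. The Table 7 row is imperfectly extracted, with action text in its grade cell, so it is weaker evidence than Table 9, although both cells point to suspension. And the numerical consequence reaches only one descriptive summary.

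**Conclusion.** The concern holds. For drug-related Grade 4 anemia, Grade 4 thrombocytopenia and Grade 3 ALT/AST unresolved at 7 days, the protocol directs both withdrawal and resumption at a lower dose, with no precedence stated. This should be fixed because it affects how patients are managed after a severe toxicity and how discontinuations are counted.

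The percentages above are upper bounds that rest on an assumed number of affected patients. No effect is claimed on the response rate, power, adverse event incidence by grade or serious adverse event counts. No view is taken on which rule is clinically right.

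**What to change.** - Reconcile Table 1 and the synopsis list with Tables 7 and 9 and sections 6.4.2 and 6.5, so that each toxicity and grade has one action, or add an explicit precedence statement. The clinical team decides which rule applies.
- Check the Grade 3 or 4 rows of Table 5 and the dose-modification Table 10 against Table 1 at the same time.
- State whether Table 1 means withdrawal from the study or from study treatment.
- Correct the cross-references in section 2.7.

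The cost is protocol amendment wording, with the IRB approval that section 13.1 requires and a check of whether the consent form is affected. Sample size and analysis do not change.
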